2.5.3. Description of the VBMI intervention

Patients enrolled will receive 60-minute sessions at Weeks 0 and 2 and four 15-minute sessions at Weeks 4, 6, 8, and 10. The sessions at Weeks 0 and 2 will focus on identifying values and creating short-term goals within those values, consistent with an ACT framework⁶. Specifically, during these first two sessions values directly (e.g., “My health is important to me.”) and indirectly (e.g., “My family is important to me, and I need to be healthy to have time for my family.”) related to health behaviors and medication adherence will be elicited. Veterans will discuss how well they are living in accordance with their stated values and identify specific goals and objectives for increasing valued living through the use of goal-setting exercises. The sessions in Weeks 4, 6, 8, and 10 will predominately be brief “check-in” meetings that will focus on helping the participant problem solve barriers to moving towards their values. For a more comprehensive description of the intervention, see Appendix F. The therapeutic approach of all sessions will be founded in MI techniques and specifically utilize the four core processes of *engaging* the Veteran to establish rapport, *focusing* the conversation on unhealthy behaviors and/or targets for change, *evoking* change-oriented talk and increased self-confidence, and *planning* specific practical steps for making change. All sessions will be conducted by a licensed psychologist who has extensive knowledge in ACT and MI or by a trained post-doctoral fellow under the supervision of a licensed psychologist. The sessions will be recorded (audio only) for the purposes of monitoring adherence of the psychologist to the VBMI protocol.

2.5.4 Description of instruments:

The **Rand-36 item Health Survey (SF-36)** is a validated instrument which evaluates physical and mental health. The 36 questions cover 8 domains: physical function, role function as limited by physical health, bodily pain, social functioning, mental health, role function as limited by emotional health, vitality and general health perception. The survey was developed by Rand Corporation as part of the Medical Outcomes Study and has been previously used in Veterans with hepatitis C.

The **Medical Outcomes Study Social Support Survey (MOS-SSS)** has also been widely used and validated among persons with chronic medical illness, including Veterans with chronic hepatitis C. This 19-item survey assesses the patients’ perceptions of their existing emotional support, tangible support, affectionate support, and social interactions.

The **Patient Health Questionnaire (PHQ-9)** is a validated survey of depressive symptoms. Higher scores indicate a greater likelihood of clinical depression. This survey is currently used to screen for depression annually in Veterans in care at VA Medical Centers.

The HCV-Treatment Self Efficacy (HCV-TSE) is a standardized survey which assesses self-belief that a patient can complete his/her treatment regimen of pegylated interferon and ribavirin. The patient rates their confidence in their ability to take medications on a scale of 0 to 10, where 0 indicates no confidence and 10 indicates full confidence. The answers to the four individual questions are averaged to a score of 0 to 10. We have adapted 4 questions from the original scale regarding medication adherence (**HCV-TSE-A**) to assess a patient's perceptions of his/her ability to adhere to DAAs.

2.5.5 Follow-up visits:

The study will last 12 weeks, with follow up visits at Weeks 2, 4, 6, 8, 10 and 12, which will be coordinated to occur on the same date as Veterans' substance abuse aftercare visits. Side effects of medications and tolerance of medications will be monitored at each visit using a single question about side effects experienced and response options including the most common side effects and a response of "other" and a description of that side effect. A single question will also be used to assess for any substance use since the last visit, with quantity and frequency being recorded if the response is positive.

Adherence will be assessed at each follow up visit using the Visual Analog Scale and pill counts. Routine laboratory monitoring will include a CBC, CHEM 14, HCV RNA and a urine sample analyzed for cocaine, marijuana, opioid, and amphetamine use (all tests are standard of care). The HCV-TSE-A will be repeated at week 4. Assessments of depressive symptoms (PHQ-9) and health-related quality of life (SF-36) will be repeated at weeks 4 and 12.

If a patient fails to complete the study, a lost to follow up form will be completed,

As part of standard of care for HCV treatment, HCV RNA is measured 12 weeks after treatment completion to assess for sustained virologic response (SVR). Although there will not be a study visit 12 weeks post treatment, this data will be collected and listed in the informed consent.

Although blood is only drawn as part of labs measured for standard of care and is not part of the study activities per se, the amount of blood drawn will not exceed 15 cc per visit.

2.5.6 Measures of adherence:

Visual Analog Scale (VAS): VAS is a self-report adherence measurement tool that is well-validated in HIV populations¹. The VAS is a 100 mm line which is anchored by word descriptions at either end.

The patient will first name his medication and the prescribed dosing intervals. The interviewer will demonstrate the equivalence of 0%, 50% and 100% adherence on the scale. The patient will then mark their level of adherence with each medication over the two-week interval. The VAS is scored by measuring the distance in mm between 0 and the patient's mark, which is recorded as % adherence. This % will be recorded at Weeks 2, 4, 6, 8, 10, and 12 for FDC MK-5172/MK-8742 (elbasvir/grazoprevir, Zepatier).

Pill Count: The number of each dispensed medications will be recorded at weeks 0, 2, 4, 6, 8, and 10. Patients will bring their pill bottles to each follow up visit where the remaining pills will be counted and recorded. Adherence will be calculated as:

$\% \text{ Adherence} = \frac{\text{number dispensed} - \text{number remaining}}{\text{number dispensed}} \times 100$

Number dispensed

3. Data Management:

Patients will be assigned a unique study number which does not contain PHI. This number will be used on all data collected for the purposes of this study. A master list of subjects which links the study number and patient identifiers will be maintained on an encrypted VA server. The data for this study will be entered into Microsoft Excel 2010. The investigator(s) and their research personnel are responsible for maintaining the study database, which will be kept on an encrypted VA server. No data will be stored on a hard drive of a PC. Only key personnel for this study will have access to the research data and access to this data will be terminated if/when the personnel are removed from the study. Research data will be maintained according to the VA records schedule. Data containing PHI will not leave the VA premises. A contract biostatistician will be used to analyze de-identified study data.

Variables/Time Points of Interest

The primary outcome of interest is the percentage of patients completing 12 weeks of treatment with FDC MK-5172/MK-8742 (elbasvir/grazoprevir, Zepatier™). Treatment completion will be defined as attendance at the last treatment visit (i.e., Week 12). Adherence will be categorized into <90% adherence and ≥ 90% adherence, based on an observed relationship between ribavirin adherence and early virologic response¹¹.

Statistical Methods

Binary logistic regression analysis will be used to report adjusted odds ratios. Differences in the distribution of HSV-TSE-A scores across categorical visits (baseline vs. Week 4) will be assessed using Wilcoxon rank sum test. In addition, parametric models (linear regression) will be explored to estimate the differences.

Power/Sample Size:

In our pilot program of 4 Veterans, we found that 75% completed 12 weeks of treatment. Estimating a 90% (18/20) completion rate in the VBMI arm, we anticipate that a sample size of 20 patients will demonstrate a trend towards higher completion rates with the VBMI intervention. We also anticipate the study will demonstrate a high rate of medication adherence. It is our intention to use data from this study to develop larger protocols with more robust sample sizes.

Limitations:

- 1) Enrollment bias may select for a different population of SUD patients than those who do not participate. We have requested approval to record demographic information from patients who do not enroll, to allow comparison for significant differences between groups in terms of age, race, gender.
- 2) Patients with NS5a mutations conferring resistance to elbasvir will require the addition of weight-based ribavirin and treatment extension to 16 weeks. Based on our current observations of patients with HCV infection and SUD, we anticipate that 47% are infected with genotype 1a. Estimating that 11% of patients with genotype 1a will have baseline NS5a resistance, we estimate that 2 patients will require 16 weeks of treatment. We will not assess

adherence beyond 12 weeks of treatment and we will not assess adherence to ribavirin in this protocol.

Adverse event reporting:

Serious and unexpected adverse events to FDC MK-5172/MK-8742 (elbasvir/grazoprevir, Zepatier™) will be reported to the IRB and Research Compliance Officer, Merck at [name] immediately upon notification and/or the FDA ([name]) or www.fda.gov/medwatch.

For events regarding data loss/theft/unauthorized access, the ISO, IRB chair, PO and RCO will be notified immediately upon notification of event.

Role of pharmacy:

The research pharmacist will store and dispense MK-5172/MK-8742 . (elbasvir/grazoprevir, Zepatier™).

If a patient fails to complete the study, a lost to follow up form will be completed.

References

9. el-Serag HB, Kunik M, Richardson P, Rabeneck L. Psychiatric disorders among veterans with hepatitis C infection. *Gastroenterology* 2002;123:476-82.

10. Sulkowski M, Hezode C, Gerstoft J, et al. Efficacy and safety of 8 weeks versus 12 weeks of treatment with grazoprevir (MK-5172) and elbasvir (MK-8742) with or without ribavirin in patients with hepatitis C virus genotype 1 mono-infection and HIV/hepatitis C virus co-infection (C-WORTHY): a randomised, open-label phase 2 trial. *Lancet*;385:1087-97.
11. Lo Re V, 3rd, Teal V, Localio AR, Amorosa VK, Kaplan DE, Gross R. Relationship between adherence to hepatitis C virus therapy and virologic outcomes: a cohort study. *Ann Intern Med* 2011;155:353-60

Amendment:

Microbiome analysis

Stool samples from patients with HCV who are on DAA therapy have been collected with their informed consent at baseline, week 4 and 12 of treatment. Stool samples are stored in -80 degree freezer, identified only by study number with no patient PHI.

16s ribosomal Bacterial DNA will be extracted from the stool samples using the *QIAamp Fast DNA Stool Mini Kit* (Qiagen) and placed into microcentrifuge tubes labeled with the study number. Bacterial DNA extraction will take place in R 403 and R 405.

The stool samples will be returned to the -80 degree freezer and will not leave the VA premises, maintaining the chain of custody.

The extracted bacterial DNA will be sent to the University of Mississippi Medical Center Molecular and Genomics Core for analysis. The bacterial DNA samples will be labeled with the study number (no PHI). The report the Core generates will also not contain PHI.

We will analyze the changes in the gut microbiome during treatment for hepatitis C. We will be able to compare baseline alpha diversity of the microbiome at week 4 and week 12 of treatment in each patient.

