Motivational interviewing (MI) was initially developed to promote abstinence in those with alcohol use disorders². In recent years, the core of MI techniques has been applied to other behavioral areas, including medication adherence³. Prior investigations have determined that MI can promote increased medication adherence among patients with HIV infection³⁻⁴, but less is known about the effect of MI on adherence to HCV medications. One prior study has associated self-efficacy, an idea conceptually linked to MI, with reduced risk of missed HCV medication doses⁵.

Acceptance and Commitment Therapy (ACT) encourages the patient to use mindfulness to promote dedication to behavioral change⁶. The patients accept the difficulties inherent to making the change and develop techniques to manage these difficulties. One major component of ACT is identifying values that make a life worth living and then mindfully moving towards such values. This approach has shown promise with tobacco use disorders⁷ and has been used to promote psychotherapy attendance among substance use disorders⁸.

We hypothesize an intervention which uses VBMI would increase rates of HCV treatment completion with FDC MK-5172/MK-8742 (elbasvir/grazoprevir, Zepatier™) among treatment naïve Veterans with HCV genotype 1 and SUD. MK-5172/MK-8742 (elbasvir/grazoprevir, Zepatier™) is a fixed dose combination once daily oral medication for chronic HCV. In clinical trials, treatment-naïve patients with genotype 1 HCV who received 12 weeks of MK-5172 and MK-8742 had sustained virologic response rates of 98%⁹.

Approximately 1 in 4 Veterans with chronic HCV have an active SUD requiring hospitalization or residential treatment¹⁰. As patients with active SUD are often excluded from clinical trial participation, examining the feasibility of using emerging DAAs in this population is warranted.

2.2 We will conduct a prospective study of **20** Veterans with treatment-naïve genotype 1 chronic hepatitis C infection admitted to the Substance Abuse Residential Rehabilitation Treatment Program (SARRTP) and/or diagnosed with SUD with ICD-10 CM code for in past 6 months. at the G.V. (Sonny) Montgomery VA Medical Center. Institutional Review Board approval will be obtained prior to the conduction of the study.

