2.5.1 Participant Recruitment and Enrollment: Veterans with active SUD are regularly screened for chronic HCV infection. All patients with chronic HCV are subsequently referred to the HCV treatment clinic for treatment evaluation. When evaluating a patient for HCV treatment, current diagnoses including SUD (ICD10 CM F10-F19) are routinely noted. It is standard of care for patients who are infected with HCV genotype 1a to undergo baseline resistance testing before initiation with MK-5172/MK-8742 (elbasvir/grazoprevir, Zepatier™). Patients meeting inclusion criteria will be offered study participation at their clinic visit. Basic demographic data (age-if less than 89 years, race, gender) will be recorded on all patients who are asked to participate in the study to allow investigators to assess for enrollment bias. Patients who agree to participate will give their written informed consent. Patients will be assigned a unique study number that does not contain personal identifiers after signing informed consent. Each patient will have only one number for the duration of the study. Study records will be labeled with this unique study number and will not contain PHI. Treatment will be prescribed in accordance with US labeling as described in the package insert.

Genotype 1b: 12 weeks MK-5172/MK-8742 (elbasvir/grazoprevir, Zepatier™)
Genotype 1a without NS5a RAVs: 12 weeks MK-5172/MK-8742 (elbasvir/grazoprevir, Zepatier™)
Genotype 1a with NS5a RAVs: 16 weeks MK-5172-MK-8742 (elbasvir/grazoprevir, Zepatier™) with weight based ribavirin

2.5.2 Baseline visit: Patients will complete a survey of demographic (age, gender, race/ethnicity, income level, marital status, education level, distance from medical center) and medical information. Drug Abuse Screening Test (DAST) and AUDIT will be completed to assess severity of SUD. We will also assess health related quality of life (Rand-36 item Health Survey [Short Form-36]), social support (Medical Outcomes Study Social Support Survey [MOS-SSS]), depressive symptoms (Patient Health Questionnaire [PHQ-9]), and treatment adherence self-efficacy (HCV Treatment Self Efficacy-A [HCV TSE-A]).

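### The pill-count formula divides by tablets dispensed rather than doses due, so an off-schedule count or a mismatched fill can put a Veteran on the wrong side of the 90% cut (minor, cheap to improve)

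*Combined protocol and SAP*

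**What the plan says.** Section 2.5.6 (Measures of adherence) sets out two measures.

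- **Pill count.** "The number of each dispensed medications will be recorded at weeks 0, 2, 4, 6, 8, and 10". Bottles come back at each follow-up visit, "where the remaining pills will be counted and recorded. Adherence will be calculated as" (number dispensed − number remaining) / number dispensed × 100.
- **Visual Analog Scale (VAS).** Veterans "mark their level of adherence with each medication over the two-week interval".

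Section 2.5.5 (Follow-up visits) has both measures taken every time: "Adherence will be assessed at each follow up visit using the Visual Analog Scale and pill counts". It places visits at Weeks 2, 4, 6, 8, 10 and 12, on dates "which will be coordinated to occur on the same date as" the Veterans' aftercare visits. No visit window, fill size or rule for leftover tablets is given.

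Section 2.1 (Background) states that the study drug "is a fixed dose combination once daily oral medication for chronic HCV". Section 2.5.1 gives the course lengths, for example "Genotype 1b: 12 weeks MK-5172/MK-8742", with a 16-week course for genotype 1a with resistance variants. Item 2 of Limitations says that adherence will not be assessed after 12 weeks of treatment.

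Variables/Time Points of Interest then states: "Adherence will be categorized into <90% adherence and ≥ 90% adherence". It does not say which measure is cut, or whether the cut applies to each interval or to the whole period. The same section defines the primary outcome by attendance at Week 12.

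**The concern.** Adherence to a once-daily drug is doses taken divided by doses due, and doses due depend on the days elapsed. The formula contains no elapsed time. If the count is early, tablets not yet due are scored as missed. If it is late and the bottle has run out, the days without tablets do not appear at all. If more is dispensed than the interval needs, or tablets are left from the previous interval, a perfect doser scores below 100% even on schedule.

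The result is then split at 90%, so a modest error can change a Veteran's category. If all 20 Veterans contribute a category, each one misclassified moves the reported proportion by 1/20 = 5 percentage points. The plan expects to show high adherence and to use the data in designing larger studies, so the figure is likely to be reported and reused.

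**Working it through.** The documents give no numerical adherence result, so there is no figure to reproduce.

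**Inputs**
- Plan's formula: 100 × (D − R)/D, with D tablets dispensed and R remaining (2.5.6).
- One dose per day (2.1), so doses due equal days elapsed: 14 in two weeks and 84 in 12 weeks. The day of first dose is day 1, and that day's dose is taken before the count.
- Cut at 90% (Variables/Time Points of Interest).
- Fill size: not stated. **Assumption:** 14 tablets per two-week fill as base case, with 16, 21 and 28 as the range.

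**Where the formula is right.** With 14 dispensed, no leftovers and a count on day 14, 0, 1 or 2 missed doses give 14/14 = 100%, 13/14 = 92.9% and 12/14 = 85.7%. These are also the doses-due values.

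**Per-interval reading, 14 tablets per fill, mid-treatment visit**

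| Count | Doses taken | Plan's formula | Doses taken / due |
|---|---|---|---|
| 1 day early, none missed | 13 | 13/14 = 92.9% | 13/13 = 100% |
| 2 days early, none missed | 12 | 12/14 = 85.7% | 12/12 = 100% |
| 1 day late, empty bottle | 14 | 14/14 = 100% | 14/15 = 93.3% |
| 2 days late, empty bottle | 14 | 14/14 = 100% | 14/16 = 87.5% |

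One day either way leaves these Veterans in the right category. Two days does not.

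**Other fill sizes.** All 14 doses taken, counted on day 14: 14/16 = 87.5%, 14/21 = 66.7%, 14/28 = 50.0%. The doses-due value is 100% each time.

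**Leftovers.** Two tablets carried over, 14 new ones, a perfect interval and two left at the count: (14 − 2)/14 = 85.7% if only the new fill is entered as dispensed, and (16 − 2)/16 = 87.5% if the leftovers are added. The doses-due value is 100%.

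**Cumulative reading, 14 tablets per fill, no dose missed.** Smallest number of days early that falls below 90%:

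| Visit | Days early | Score | One day fewer |
|---|---|---|---|
| Week 4 | 3 | 25/28 = 89.3% | 26/28 = 92.9% |
| Week 6 | 5 | 37/42 = 88.1% | 38/42 = 90.5% |
| Week 8 | 6 | 50/56 = 89.3% | 51/56 = 91.1% |
| Week 10 | 8 | 62/70 = 88.6% | 63/70 = 90.0% |
| Week 12 | 9 | 75/84 = 89.3% | 76/84 = 90.5% |

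**Missing supply on the cumulative reading.** If the Week 10 fill is missed and the count is on day 84, the plan's formula gives 70/70 = 100%, against 70/84 = 83.3% of doses due.

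**The case against.** The case for leaving the formula alone is reasonable. Dispensing and counting follow the same two-week grid. If each fill matches its interval and visits are on time, the formula is exact. For misclassification, a count must be off schedule or a fill mismatched, and the 90% cut must be applied to the pill count rather than the VAS. For small timing errors, the reading must also be per interval. The documents settle none of these. Read cumulatively, a fully adherent Veteran is misplaced at Week 12 only if counted by day 75, five days after a nominal Week 10 visit. Simply stating that the cut is cumulative would remove most of the early-count problem.

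All of that stands, and it limits the point to a minor one. What it does not answer is missing supply. Cumulating leaves a missed last fill at 70/70 = 100%, and only a doses-due denominator corrects it.

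A reader might also infer that every empty bottle at a late visit is an error. That is not so at the end of a 12-week course: a Veteran who has taken all 84 doses and is counted late at Week 12 is correctly scored 100%.

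**Conclusion.** The point holds as a minor, inexpensive improvement. The formula measures share of supply used, and it can place a Veteran on the wrong side of 90%. With 14 tablets per fill, a 2-day timing error is enough per interval, while a fully adherent Veteran counted cumulatively at Week 12 must be counted 9 days early. Larger fills misstate adherence per interval even on schedule. These sizes rest on the assumed fill sizes and on the cut being applied to the pill count.

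Three stronger conclusions are tempting and not supported:
- **That the main result is compromised.** The primary outcome is Week 12 attendance, no listed hypothesis uses the pill count, and the VAS does not depend on tablets dispensed.
- **That reported adherence will be inflated, or deflated.** Early counts and surplus supply lower the score, while late counts with an empty bottle raise it. The documents do not show how often either will occur, so the net direction is unknown.
- **That the 90% category feeds a formal test, or that it is purely descriptive.** The logistic regression in Statistical Methods names no outcome, so neither can be established.

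**What to change.** **In 2.5.6**, replace the formula with:

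(cumulative tablets dispensed before the count − tablets remaining at the count) / doses due × 100, capped at 100%.

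Doses due are the days from first dose to the actual count date, at one per day, with a maximum of 84 for every Veteran. The maximum follows from Limitations item 2, which ends adherence assessment at 12 weeks, so it also applies to those on the 16-week course.

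**In Variables/Time Points of Interest**, state that the <90%/≥90% category uses this cumulative pill-count figure and that the VAS is reported separately. Show alongside it the number of Veterans whose last count is before Week 12: someone lost after a perfect Week 2 would otherwise appear simply as 14/14 = 100%.

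**Checks (14 tablets per fill)**
- Perfect dosing, counted on day 75: 75/75 = 100%.
- All 84 doses taken, counted on day 94: 84/84 = 100%.
- Eight doses missed, counted on day 85: 76/84 = 90.5%.
- Week 10 fill missed, counted on day 84: 70/84 = 83.3%.

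**Cost.** One formula and a few sentences. Dispensed and remaining counts are already collected; the dates of first dose and of each count must be recorded with them. There is one weakness: if the final count falls after day 84, tablets taken after day 84 are credited. A Veteran without tablets for 10 days who receives the Week 10 fill on day 80 has taken 70 + 4 = 74 doses by day 84 (74/84 = 88.1%), but scores 84/84 = 100% if counted on day 94. The gap then shows only in the earlier count (70/80 = 87.5% at the Week 10 visit held on day 80), so the earlier counts should be kept as descriptive data.

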Title: Evaluating values-based motivational interviewing to increase treatment completion with fixed dose combination MK-5172/MK-8742 among Veterans with active substance use disorders and treatment-naïve genotype 1 chronic hepatitis C

Investigators: [name] [name]., [name].,

1. Objective and hypotheses.

Primary Objective: Implement a values-based motivational interviewing (VBMI) intervention to promote treatment completion with fixed dose combination (FDC) MK-5172/MK-8742 (elbasvir/grazoprevir, Zepatier™) x 12 weeks among treatment-naïve Veterans with substance use disorder (SUD) and genotype 1 chronic hepatitis C virus (HCV) infection.

Primary Hypothesis: Veterans with SUD and genotype 1 chronic HCV infection who receive the VBMI intervention will complete the full course of treatment in 90% of cases.

Secondary Objectives:

- 1) Utilize VBMI to promote self-efficacy in taking FDC MK-5172/MK-8742 (elbasvir/grazoprevir, Zepatier™) among Veterans with active SUD and chronic HCV infection.
- 2) Demonstrate the feasibility of FDC MK-5172/MK-8742 (elbasvir/grazoprevir, Zepatier™) for obtaining sustained virologic response (SVR) in treatment-naïve genotype 1 chronic HCV infection among Veterans with active SUD.
- 3) Measure the prevalence of baseline NS5a resistance mutations in Veterans with active SUD and genotype 1a chronic HCV infection. NS5a is a nonstructural HCV protein.

Secondary Hypotheses:

- 1) Veterans with SUD enrolled in this study will demonstrate a trend towards clinically significant increases in HCV treatment adherence self-efficacy scores between baseline and week 4 of treatment.
- 2) FDC MK-5172/MK-8742 (elbasvir/grazoprevir, Zepatier™) will be well-tolerated by Veterans with SUD.

2. Study procedures

2.1 Background: The advent of direct acting antivirals (DAAs) for chronic HCV infection has increased the tolerability and effectiveness of curative HCV treatment. Disorders which can affect adherence to HCV treatment, including SUD, can reduce effectiveness of DAAs. During the pegylated interferon era, the VA HCV 001 study group demonstrated an association

between recent alcohol use and early treatment discontinuation, resulting in decreased treatment efficacy¹. The authors concluded that patients with alcohol use should be provided additional support to assist with treatment completion.

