2.3.1 Study Population

The G.V. (Sonny) Montgomery VAMC is an urban, academically-affiliated medical center in the Southeastern United States. . The center provides care to approximately 39,000 unique Veterans annually in rural and urban areas of Mississippi and surrounding states. The hepatitis clinics in the facility meet 3 ½ days weekly and, to date, have provided DAAs to over 600 Veterans with chronic HCV. As part of a pilot treatment program, 4 Veterans initiated HCV treatment while in residential treatment for SUD. Of these, 3 completed all 12 weeks of treatment while 1 relapsed into alcohol abuse and was lost to follow up.

The HCV treatment clinics meet 3 ½ days weekly to provide DAA treatment for HCV. Veterans with co-existing MH conditions are frequently seen in clinic, including active SUD. Active SUD is not a contraindication for treatment provided the Veteran demonstrates he/she can adhere to medications and follow up visits. Patients with active SUD who begin DAA treatment as an outpatient are followed every 2 weeks.

Inclusion criteria:

- 1) Identified as having treatment-naïve genotype 1 chronic HCV infection; Veterans who are genotype 1a must have baseline NS5a resistance testing
- 2) Current resident of the SAR RTP program and/or ICD-10 CM code for SUD (F10-F19) within the past 6 months
- 3) Willing to initiate treatment with FDC MK-5172/MK-8742 (elbasvir/grazoprevir, Zepatier™)

Exclusion criteria:

- 1) Contraindications for therapy with FDC MK-5172/MK-8742 (elbasvir/grazoprevir, Zepatier™)
- 2) Unable to provide written informed consent
- 3) Hepatocellular carcinoma or other medical condition precluding HCV treatment
- 4) Acute HCV infection
- 5) Prior treatment for chronic HCV
- 6) History of decompensated cirrhosis
- 7) Platelet count < 75 K/cmm and/or albumin < 3 grams/dL
- 8) Females and male sex partners of females who are pregnant, nursing and/or unwilling to use contraception
- 9) Patients infected with genotype 1a who have not undergone baseline NS5a resistance testing

See attached flow chart.

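### The primary outcome is a single-group completion percentage, but the only binary-outcome method stated is logistic regression with adjusted odds ratios, and no interval for the percentage is planned

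*Combined protocol and SAP*

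**What the plan says.** Under Variables/Time Points of Interest: "The primary outcome of interest is the percentage of patients completing 12 weeks of treatment". Completion means attending the Week 12 visit, and this point takes that definition as it stands. The Primary Hypothesis is that Veterans given VBMI "will complete the full course of treatment in 90% of cases".

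There is one group. Section 2.2 describes a prospective study of 20 Veterans, and section 2.5.3 gives the intervention to everyone: "Patients enrolled will receive 60-minute sessions at Weeks 0 and 2 and four 15-minute sessions".

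Statistical Methods has three sentences. The first is "Binary logistic regression analysis will be used to report adjusted odds ratios". The other two (a Wilcoxon rank sum test and linear regression) concern self-efficacy scores at baseline and Week 4. The logistic sentence names no outcome, exposure or covariates. No confidence interval or other measure of precision for the completion percentage appears anywhere in the document.

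Power/Sample Size sets the anticipated result beside the pilot: "Estimating a 90% (18/20) completion rate in the VBMI arm", and then "we anticipate that a sample size of 20 patients will demonstrate a trend towards higher completion rates with the VBMI intervention". The pilot is described in section 2.3.1: "Of these, 3 completed all 12 weeks of treatment while 1 relapsed into alcohol abuse and was lost to follow up". The stated use of the results is this: "It is our intention to use data from this study to develop larger protocols with more robust sample sizes".

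**The concern.** The question asked and the method named do not fit each other. The question is what fraction of one treated group completes. The method describes how the odds of some binary outcome vary with covariates. There are three ways to read the logistic sentence, and none supplies what the primary outcome needs:

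- **Effect of VBMI on completion.** This cannot be estimated within the study, because no enrolled patient is unexposed.
- **Predictors of completion.** The model would rest on the non-completers, of whom the plan expects about 2.
- **Another binary outcome, such as adherence split at 90%.** The model then does not bear on completion, and the primary outcome is left with a bare percentage.

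What is at stake is the use made of the result. A completion rate reported without its uncertainty would feed the design of larger studies. A bare 90% printed beside 75% would also invite a claim of improvement that 20 patients and a pilot of 4 cannot carry.

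**Working it through.** **Inputs.** Enrolled n = 20, one group (sections 2.2 and 2.5.3). Anticipated completers 18 (Power/Sample Size). Target 90% (Primary Hypothesis). Pilot 3 of 4 (section 2.3.1 and Power/Sample Size). The documents give no confidence level, so two-sided 95% is assumed.

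**1. The plan's own figures.** 18/20 = 0.90 and 3/4 = 0.75, as stated, a difference of 15 percentage points. The size of 20 cannot be reproduced from a power calculation, because no significance level, sidedness, power or test is given.

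**2. Precision of the anticipated result.** The exact (Clopper-Pearson) limits for x completers out of n are the 0.025 quantile of Beta(x, n − x + 1) and the 0.975 quantile of Beta(x + 1, n − x).

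- For 18/20, Beta(18, 3) gives 0.683 and Beta(19, 2) gives 0.988, so **68.3% to 98.8%**.
- Wilson, with z² = 3.8415: centre 0.9 + 3.8415/40 = 0.9960; half-width 1.96 × √(0.9 × 0.1/20 + 3.8415/1600) = 0.1628; divisor 1 + 3.8415/20 = 1.1921. The limits are (0.9960 ∓ 0.1628)/1.1921, or 69.9% to 97.2%.

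Both intervals contain 90% and 75%. Exact intervals for other possible results:

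| Completers | Rate | Exact 95% CI |
|---|---|---|
| 15/20 | 75% | 50.9% to 91.3% |
| 17/20 | 85% | 62.1% to 96.8% |
| 19/20 | 95% | 75.1% to 99.9% |
| 20/20 | 100% | 83.2% to 100% |

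Only 19 or 20 completers would put the lower limit above 75%, and then only if 75% were a known constant.

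**3. Precision of the pilot.** It is not a known constant. For 3/4, the lower limit from Beta(3, 2) is 0.194 and the upper limit is 0.975^(1/4) = 0.994, so **19.4% to 99.4%**. That excludes almost nothing.

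**4. The two together, for illustration.** The Newcombe interval for 18/20 minus 3/4 uses the Wilson limits (0.6990 to 0.9721, and 0.3006 to 0.9544):

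- lower: 0.15 − √[(0.9 − 0.6990)² + (0.9544 − 0.75)²] = 0.15 − 0.287 = −0.137
- upper: 0.15 + √[(0.9721 − 0.9)² + (0.75 − 0.3006)²] = 0.15 + 0.455 = 0.605

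The 15-point difference is compatible with anything from −13.7 to 60.5 points.

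**5. The logistic model, if applied to completion.** Non-completers expected: 20 − 18 = 2. To show what that means, assume a single binary covariate split 10/10 and unrelated to completion (the documents specify no covariates). Both non-completers fall in the same half, leaving a zero cell and no finite ordinary estimate, with probability 2 × C(10,2)/C(20,2) = 90/190 = 47%. With 5 non-completers (75% completion) it is 2 × C(10,5)/C(20,5) = 504/15,504 = 3%. The difficulty is marked at the plan's own 90% and much milder at 75%. It arises with one predictor, so limiting the model to one predictor does not remove it.

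**The case against.** The best defence is that this is a 20-patient feasibility study with a descriptive target. Computing the percentage is itself the analysis that matches the 90% hypothesis, anyone given the count can work out the interval, and the plan claims only a trend while deferring firm conclusions to larger protocols. The logistic sentence follows directly after the adherence categories and may never have been meant for completion.

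Much of this stands, and it rules out several stronger readings:

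- A reader might infer that the 90% hypothesis has no analysis at all. The documents do not support that. The percentage is planned; its precision is not.
- A reader might infer that logistic regression is the declared primary analysis and will fail. The sentence names no outcome, so the problem with 2 non-completers is conditional, and the zero-cell figures rest on an assumed covariate.
- A reader might infer from the reference to a VBMI arm that a control arm exists, or that a formal test against the pilot is promised. Neither is in the document.
- A reader might infer bias. A missing interval that can be recovered from the reported count is a gap in the plan, not a bias.

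It might also be said that a logistic model with no covariates yields a proportion and its interval. True, but the plan asks for adjusted odds ratios, which are a different quantity.

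The defence does not dispose of the point. The main product of a small study is an estimate, and at n = 20 its precision decides how far it can be used. The plan did choose a method, and the method does not address the primary outcome. It also says that 20 patients will show a trend, which its own anticipated result would not support.

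**Conclusion.** The concern holds as a mismatch between outcome and method, together with an unplanned interval. On any reading, the stated logistic regression gives neither the completion percentage nor its precision, and it cannot give a VBMI effect. If it is applied to completion at the anticipated rate, about 2 non-completers cannot support reliable adjusted odds ratios.

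The interval at 18/20 is about 30 percentage points wide (98.8 − 68.3 = 30.5), covers the target and the pilot rate alike, and sits beside a pilot interval of about 80 points (99.4 − 19.4 = 80.0). A trend over the pilot would not be supported even if the study turns out exactly as anticipated.

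The conclusion rests on an assumed two-sided 95% level and on the anticipated count. The exact and Wilson methods lead to the same reading. The point should be corrected before analysis, and correcting it is easy.

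**What to change.** In Statistical Methods:

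- Make the primary analysis the number attending Week 12 divided by the number enrolled, with patients lost to follow-up counted as non-completers, and a 95% confidence interval by the exact (Clopper-Pearson) or Wilson method. Choose one in advance. Use the number actually enrolled, not a fixed 20.
- Report SVR the same way, with a stated rule for missing results. Section 2.5.5 says there is no study visit 12 weeks after treatment and that this result comes from routine care, so some may be missing.
- Show the pilot's 3/4 only descriptively, with its own interval, and make no claim of effect. Reword the trend statement in Power/Sample Size to match.
- Name the outcome and covariates of the logistic model and label it exploratory. If it is applied to completion, use a Firth-penalised or exact method.

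The cost is a few sentences, plus the rule for missing SVR results. No new data, visits or patients are needed. The downside is presentational: the completion rate appears with a wide interval, and the odds ratios become exploratory.
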